#### **Censoring**

Patients will be censoring if they did not discontinue their index treatment but had an occurrence of any of the following: 365 days of follow-up without discontinuation, death, disenrollment, end of data.

#### **9.3.2.2 Secondary outcomes**

Not applicable.

#### **9.3.3 Covariates**

Covariates will be identified based on data recorded within 180 days prior to or on the index date (date of dispensing/initiation of the exposure), unless otherwise specified. If multiple measurements are made in the baseline period, then the most recent measurement will be used.

Covariates will be used to predict propensity scores in later analyses. Absolute and relative frequencies of each covariate will also be reported in Table Shells 1 and 2 (see [Annex 5](#)). Detailed descriptions of the listed covariates can be found in [Annex 3](#) and [4](#).

#### **Demographics**

- Age on index date
- Sex (Male, Female)
- Region (Northeast, North Central, South, West, Unknown, Missing)
- Insurance Type (Commercial, Medicare, Missing)
- Year of Cohort Entry (First Year, Second Year)

#### **Concomitant Medications**

- Oral Corticosteroids
- Short acting muscarinic antagonist (SAMA)
- Short acting beta agonist (SABA)
- Long acting muscarinic antagonist (LAMA)
- Long acting beta agonist (LABA)
- Inhaled corticosteroid (ICS)
- LAMA / LABA combination (that is not Stiolto or Anoro)
- LABA / ICS combination
- LAMA / LABA / ICS combination
- NSAIDs
- Antihistamines
- Opioids
- Oral antibiotics
- Antidiabetic Agents (not including insulin)

- Insulin (basal or mealtime)
- Methotrexate
- Statins
- Antihypertensives
- Anticoagulants
- Anti-psychotic/anti-depressives/anxiolytic
- Oxygen therapy

**Comorbidities/Symptoms**

- History of All-Cause Hospitalization
- History of Emergency Department Visit
- History of Hospitalization due to Respiratory Condition
- Acute Myocardial Infarction
- Angina Pectoris
- Peripheral Vascular Disease
- Heart Failure
- Hypertension
- Upper Respiratory Infection
- Lower Respiratory Infection
- Cardiac Arrhythmias
- Cerebrovascular Disease
- All Cancers (except nonmelanoma skin cancer)
- Allergic Rhinitis
- Chronic Sinusitis
- Bronchiectasis
- Pneumonia
- Chronic Bronchitis
- Exertional Breathlessness
- Anxiety
- Dementia
- Depression
- Osteoporosis
- Charlson Deyo Comorbidity Index
- Acute Liver Injury or Failure
- Chronic Kidney Disease (without ESRD)
- End Stage Renal Disease
- Rheumatic Disease
- Peptic Ulcer Disease
- Gastroesophageal Reflux Disease
- Type 1 Diabetes Mellitus
- Type 2 Diabetes Mellitus
- HIV/AIDS
- Hemiplegia or Paraplegia

**Lifestyle**

- Smoking-related claim
- Vaccination for Influenza
- Vaccination for Pneumococcus

**Respiratory Function Procedures/Tests**

- Pulmonary function tests
- Six-minute walk test
- Chest X-ray
- High resolution chest CT

**9.4 DATA SOURCES**

The proposed study will utilize data from Truven MarketScan data (US).

The Truven MarketScan databases capture longitudinal, individual-level administrative claims data from the United States. The data available for the study includes three components of MarketScan: the Commercial Claims and Encounters (CCAE) Database, the Medicare Supplemental and Coordination of Benefits Database (MDCR), and the Medicaid Database. Patients in the databases include active employees, dependents, retirees, COBRA recipients, and Medicare or Medicaid enrollees. Data were drawn from large employers, health plans, and public organizations in the United States. The following tables of the MarketScan databases were available for analysis: Enrollment Detail, Inpatient Admissions, Inpatient Services, Outpatient Services, Outpatient Pharmaceutical Claims, and Long Term Care. These tables provide information on plan enrollment, healthcare utilization and expenditures, demographics, and integrated records for inpatient events, outpatient events, and pharmacy dispensings. Data are available from January 1, 2008 to March 31, 2018, and represent approximately 162 million patients.

**9.5 STUDY SIZE**

There are 14,751 new users of Olodaterol/Tiotropium Bromide or Umeclidinium/Vilanterol between 17 November 2015 and 31 March 2018 who satisfied the inclusion criteria. Among them, 3,889 initiated Olodaterol/Tiotropium Bromide and 10,862 initiated Umeclidinium/Vilanterol).

**9.6 DATA MANAGEMENT****Dataset**

The Truven Health MarketScan database is comprised of fully adjudicated and paid claims records of integrated longitudinal enrolment, inpatient, outpatient and drug data from multiple payors that has been standardized and de-identified prior to use for the analysis. The statistical analysis will be conducted using the Evidence Platform.

## Drug Duration

Unless otherwise noted, drug event duration was calculated from the “Day’s Supply” field, and in cases where this field was 0, the duration was assumed to be 1 day.

## Handling of Missing Data

Missing data that occurs in covariates or descriptive variables will be classified as its own level. In addition, a feasibility assessment before beginning the analyses will be done, and variables with >75 % missing values will be excluded from all analyses, other than baseline characteristics. If a variable is left with only one level other than missing, the variable will be excluded completely from all analyses.

## 9.7 DATA ANALYSIS

### 9.7.1 Main analysis

For all analyses, variables will be reported as follows:

- Continuous variables (e.g., age) will be presented as means (with standard deviation, SD) and/or medians (with interquartile range, IQR).
- Categorical variables (e.g., sex) will be presented as absolute and relative frequencies.
- All results will have two digits following the decimal point.

#### 9.7.1.1 Descriptive Analysis

All variables specified in [section 9.3.3](#) will be reported. For demographic and lifestyle variables, the value recorded on the cohort entry date will be reported, otherwise the most recent known value will be reported. Presence of comorbidities and use of concomitant medication use will be determined based whether they ever occurred within the 180-day baseline period preceding the index date. Differences in the confounder distributions were inspected for successful confounder balance of measured characteristics.

#### 9.7.1.2 Rates and Risks

- Rate of Discontinuation of Olodaterol/Tiotropium Bromide or Umeclidinium/Vilanterol in the Pre-matched Cohort

Among the pre-matched cohort, rates of discontinuation of Olodaterol/Tiotropium Bromide or Umeclidinium/Vilanterol will be reported as the number of events divided by the number of person-years at risk.

- Risk of Discontinuation of Olodaterol/Tiotropium Bromide or Umeclidinium/Vilanterol in the Pre-matched Cohort

Among the pre-matched cohort, risk (proportion of patients) of discontinuation of Olodaterol/Tiotropium Bromide or Umeclidinium/Vilanterol will be reported as the number of events divided by the number of eligible patients at cohort entry date.

- Discontinuation of Olodaterol/Tiotropium Bromide or Umeclidinium/Vilanterol in the Post-matched Cohort

Among the post-matched cohort, rates of discontinuation of Olodaterol/Tiotropium Bromide or Umeclidinium/Vilanterol will be reported as the number of events divided by the number of person-years at risk.

- Discontinuation of Olodaterol/Tiotropium Bromide or Umeclidinium/Vilanterol in the Post-matched Cohort

Among the post-matched cohort, risk (proportion of patients) of discontinuation of Olodaterol/Tiotropium Bromide or Umeclidinium/Vilanterol will be reported as the number of events divided by the number of eligible patients at cohort entry date.

#### 9.7.1.3 Comparative Persistence

- Relative Rate of Discontinuation of Olodaterol/Tiotropium Bromide vs Umeclidinium/Vilanterol in the Unmatched Cohort

Multivariable Cox proportional hazards models with all variables (except components of the Charlson Comorbidity index) in [section 9.3.3.](#) will be used to estimate the hazard ratios (HRs) and 95% CIs for Olodaterol/Tiotropium Bromide compared to patients treated with Umeclidinium/Vilanterol during follow-up for incident discontinuations, according to the following model:

$$h(t | \text{Treatment}, X_1, \dots, X_n) = h(t_0) * \exp(\beta_1 * \text{Treatment} + \beta_2 * X_2 + \dots + \beta_n * X_{n+1})$$

Where treatment can be 1=Stiolto or 0=Anoro and t = time to discontinuation

- Relative Risk of Discontinuation of Olodaterol/Tiotropium Bromide vs Umeclidinium/Vilanterol in the Unmatched Cohort

Multivariable logistic regression will be used to assess relative risk of discontinuation and 95% CIs for Olodaterol/Tiotropium Bromide compared to patients treated with Umeclidinium/Vilanterol during follow-up for incident discontinuations, according to the following model using all covariates (except components of the Charlson Comorbidity index) in [section 9.3.3.](#):

$$\text{Logit}(\text{Discontinuation}=1 | \text{Treatment}, X_1, X_2, \dots, X_n) = \beta_0 + \beta_1 * \text{Treatment} + \beta_2 * X_2 + \dots + \beta_n * X_{n+1}$$

- Relative Rate of Discontinuation of Olodaterol/Tiotropium Bromide vs Umeclidinium/Vilanterol in the Matched Cohort

Cox proportional hazards models with treatment as the only independent variable will be used to estimate the hazard ratios (HRs) and 95% CIs for Olodaterol/Tiotropium Bromide

compared to patients treated with Umeclidinium/Vilanterol during follow-up for incident discontinuations, according to the following model:

$$h(t | \text{Treatment}, X) = h_0(t) * \exp(\beta_1 * \text{Treatment})$$

Where treatment can be 1=Stiolto or 0=Anoro and t = time to discontinuation

- Relative Risk of Discontinuation of Olodaterol/Tiotropium Bromide vs Umeclidinium/Vilanterol in the Matched Cohort

Logistic regression will be used to assess relative risk of discontinuation and 95% CIs for Olodaterol/Tiotropium Bromide compared to patients treated with Umeclidinium/Vilanterol during follow-up for incident discontinuations, according to the following model:

$$\text{Logit}(\text{Discontinuation}=1 | \text{Matched set}) = \beta_1 * \text{Treatment} + \alpha_{\text{stratum}(i)}$$

Where treatment can be 1=Stiolto or 0=Anoro and t = time to discontinuation

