Name of company: Boehringer Ingelheim International GmbH			
Name of finished medicinal product: Stiolto® Respimat®; Anoro® Ellipta®			
Name of active ingredient: Olodaterol and Tiotropium Bromide (ATC R03AL06); Umeclidinium and Vilanterol (ATC R03AL03)			
Protocol date: 22 November 2019	Study number: 1237-0090	Version/Revision: 1.0	Version/Revision date: NA
Data sources:	Truven MarketScan is a claims database that captures longitudinal, individual-level administrative claims data from the United States.		
Study size:	There are 14,751 new users of Olodaterol/Tiotropium Bromide or Umeclidinium/Vilanterol between 17 November 2015 and 31 March 2018 who satisfied the inclusion criteria. Among them, 3,889 initiated Olodaterol/Tiotropium Bromide and 10,862 initiated Umeclidinium/Vilanterol).		
Data analysis:	
For demographic and lifestyle variables, the value recorded on the cohort entry date will be reported, otherwise the most recent known value will be reported. Presence of comorbidities and use of concomitant medication use will be determined based whether they ever occurred within the 180-day baseline period preceding the index date. Differences in the confounder distributions will be inspected for successful confounder balance of measured characteristics.
 
Patients will be followed up until first occurrence of death, discontinuation, disenrollment, end of data, or 365 days.
 
The data will be displayed in a nonparametric fashion on a persistency curve (a Kaplan–Meier curve) with discontinuation considered as elimination.
 
Unmatched Cohort Rates and risks (proportion of patients) with the outcomes for each exposure group will be reported among the unmatched cohort.
 
Matched Cohort Rates and risks (proportion of patients) with the outcomes for each exposure group will be reported among the matched cohort.
 
Logistic regression will be used to calculate the propensity to initiate Olodaterol/Tiotropium Bromide versus Umeclidinium/Vilanterol. The propensity score will then be used to identify up to 2 initiators of Umeclidinium/Vilanterol for each initiator of Olodaterol/Tiotropium Bromide with the same propensity score (<math>\pm</math> a caliper of 5%) as the corresponding initiator of Olodaterol/Tiotropium Bromide.
		

Name of company: Boehringer Ingelheim International GmbH			

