Name of finished medicinal product: Stiolto® Respimat®; Anoro® Ellipta®			
Name of active ingredient: Olodaterol and Tiotropium Bromide (ATC R03AL06); Umeclidinium and Vilanterol (ATC R03AL03)			
Protocol date: 22 November 2019	Study number: 1237-0090	Version/Revision: 1.0	Version/Revision date: NA

Cox proportional hazard regression model will be used to assess the relative rate (or hazard) of the outcome in patients treated with Olodaterol/Tiotropium Bromide compared to patients treated with Umeclidinium/Vilanterol during the one-year follow-up. Crude HRs and 95% CIs will be reported for the matched cohorts.
 
Among the matched cohort, relative risks with 95% CIs will also be reported, as assessed by conditional logistic regression.
 
Relative rates and risks will also be reported using standard multivariable regression.
 
Sensitivity Analyses
 
 
• Restrict the 60-day allowable grace period used to define the discontinuation outcome to 30 days.
 
• Increase the 60-day allowable grace period used to define the discontinuation outcome to 90 days.
 
• Start the patient identification period on 21 May 2015 immediately upon FDA approval.
 
• Exclude patients with ACOS. Patients with asthma only but not COPD are still excluded from cohort.
 
			
Milestones:	
 
- Feasibility assessment Sept 2018 (done)
 
- Draft study protocol Dec 2018
 
- Final study protocol Apr 2019
 
- Results tables available May 2019
 
- 1st Abstract submitted (ERS 2019, ISPOR or AMCP ) Jun 2019
 
- Manuscript submitted Q2 2019
 
		

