## Study timeline for the Primary Study Population

## 9.2.2 Study population

The pre-matched study cohort will consist of patients initiating Olodaterol/Tiotropium Bromide or Umeclidinium/Vilanterol between 17 November 2015 and 31 March 2018.

The following exclusion criteria will then be applied:

Aged <40 years.

Enrolment with medical and pharmacy coverage prior to the cohort entry < 180 days.

Never had COPD diagnosis on the cohort entry date or prior to cohort entry.

A record for dispensed Olodaterol/Tiotropium Bromide delivered with Respimat inhalator or Umeclidinium/Vilanterol delivered with the Ellipta Inhaler during the 180-day baseline prior to cohort entry.

[figure not shown]
Diagnosis of asthma any time prior to cohort entry.

Diagnosis of lung cancer any time prior to cohort entry.

Diagnosis of lung transplant any time prior to cohort entry.

Figure 2

Below depicts the flow diagram of patients.

Diagnosis of COPD (ICD-9: 491.\*, 492.\*, 496.\*; ICD-10: J41.0, J41.1, J41.8, J42.\*, J43.0, J43.1, J43.2, J43.8, J43.9, J44.0, J44.1, J44.9) will be defined as the presence of an inpatient or outpatient claim.

Diagnosis of asthma (ICD-9: 493.\*; ICD-10: J45, J45.20, J45.21, J45.22, J45.90\*, J45.99\*) will be defined as either 1 inpatient claim or 2 outpatient events 30-365 days apart.

Diagnosis of lung cancer (ICD-9: 162.2, 162.3, 162.4, 162.5, 162.8, 162.9, 231.2; ICD-10: C34.00, C34.01, C34.02, C34.10, C34.11, C34.12, C34.2, C34.30, C34.31, C34.32, C34.80, C34.81, C34.82, C34.90, C34.91, C34.92, C7A.090, D02.20, D02.21, D02.22, Z85.118) will be defined as either 1 inpatient claim or 2 outpatient events 30-365 days apart.

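### Logistic results named relative risk are odds ratios, and the planned risk (events over all entrants) is a crude proportion below the 365-day risk; secondary outputs only

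*Combined protocol and SAP*

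**What the plan says.** **Relative risk.** For the unmatched cohort, Section 9.7.1.3 says "Multivariable logistic regression will be used to assess relative risk of discontinuation and 95% CIs for Olodaterol/Tiotropium Bromide", followed by a logit model with treatment and covariates. For the matched cohort it gives a logit model with a term for each matched set, again under a relative-risk heading. The abstract agrees: "Among the matched cohort, relative risks with 95% CIs will also be reported, as assessed by conditional logistic regression". No step turns either coefficient into a risk ratio. Tables 4 and 5 (Annex 5) have a Risk Ratio row and no odds-ratio row.

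**Risk.** Section 9.7.1.2 says that risk "will be reported as the number of events divided by the number of eligible patients at cohort entry date", in both cohorts. On follow-up the abstract says: "Patients will be followed up until first occurrence of death, discontinuation, disenrollment, end of data, or 365 days". The cohort is "patients initiating Olodaterol/Tiotropium Bromide or Umeclidinium/Vilanterol between 17 November 2015 and 31 March 2018" (Section 9.2.2), and Section 9.4 puts the end of the data on that same 31 March 2018. Enrolment is required for 180 days before entry; no minimum follow-up afterwards is stated.

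**Estimates that allow for censoring.** Person-year rates, Cox hazard ratios (the primary estimates in Tables 4 and 5) and a Kaplan-Meier display are planned. On the last, the abstract says: "The data will be displayed in a nonparametric fashion on a persistency curve".

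**Table shells.** In Tables 4 and 5 risk is per 1,000 patients, but the risk difference below it is per 1,000 person-years with a reference value of 1.0.

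**The concern.** The exponentiated coefficient of a logit model, conditional or not, is an odds ratio. It lies further from 1 than the risk ratio unless the event is rare, and the plan nowhere says that discontinuation is rare. A reader told that the result is a relative risk would overstate the difference between the inhalers.

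Events over all entrants equals the 365-day risk only if nobody is censored before day 365. The entry and data-end dates rule that out for late entrants, and disenrollment adds to the shortfall. Patients entering near the end of the data are in the denominator with little or no chance of entering the numerator. The two logistic models use the same yes/no outcome regardless of follow-up time.

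Risk by arm in the matched cohort and adjusted relative risk in the unmatched cohort are secondary objectives in the abstract. Section 9.7.2 also repeats Tables 4 and 5 in every sensitivity analysis, including those with 30- and 90-day grace periods. The grace period itself changes how many late entrants can have an event, so differences in events/N between those analyses would partly reflect truncated follow-up.

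**Working it through.** **Inputs from the documents.** 3,889 and 10,862 initiators (Section 9.5): 3,889 + 10,862 = 14,751, as stated. Entry runs from 17 November 2015 to 31 March 2018 and data end on 31 March 2018. Follow-up is capped at 365 days and the grace period is 60 days. On days' supply: "in cases where this field was 0, the duration was assumed to be 1 day".

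**Assumptions, none in the documents.** Discontinuation risk, uniform entry, hazard shape, disenrollment and mortality.

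**1. Odds ratio against risk ratio.** With reference risk p0 and p1 = 1.10 × p0, OR = [p1/(1−p1)] / [p0/(1−p0)].

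| p0 | p1 | Risk ratio | Odds ratio |
|---|---|---|---|
| 5% | 5.5% | 1.10 | 1.11 |
| 30% | 33% | 1.10 | 1.15 |
| 50% | 55% | 1.10 | 1.22 |
| 60% | 66% | 1.10 | 1.29 |

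For example, at 60%: (0.66/0.34)/(0.60/0.40) = 1.941/1.5 = 1.29.

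**2. Entry days.** The window has 866 days. Entry up to 31 March 2017 (501 days) allows 365 days of data; the other 365 days do not: 365/866 = 42%. An event needs at least 1 day of supply plus the 60-day gap, so entrants in the last 60 days cannot have one: 60/866 = 6.9%, and 14,751 × 60/866 ≈ 1,020 patients. With a 30-day first fill this becomes the last 90 days: 90/866 = 10.4%, about 1,530 patients.

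**3. Reported proportion.** Average P(event by min(365, days to data end − g)) over entry days, with cumulative hazard proportional to (t/365)^k. Here k = 1 is a constant hazard and k = 0.5 a front-loaded one. Setting g = 60 requires the gap to be observed. Setting g = 0 ignores that requirement and so credits events to entrants who cannot have one; it is an upper bound.

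For a true 365-day risk of 60% and k = 1, entrants with truncated follow-up average 0.344:
- g = 0: (501 × 0.60 + 365 × 0.344)/866 = 0.49.
- g = 60: (441 × 0.60 + 365 × 0.344 + 60 × 0)/866 = 0.45.

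| True risk | k = 1: g = 60 to g = 0 | k = 0.5: g = 60 to g = 0 |
|---|---|---|
| 30% | 22-24% | 24-26% |
| 60% | 45-49% | 49-53% |

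Adding 20% yearly disenrollment (k = 1), 60% becomes 40-45%.

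**4. Effect on contrasts.** Take the same entry pattern in both arms, a hazard ratio of 1.25 and a comparator risk of 60%. The other arm's risk is 1 − 0.40^1.25 = 68.2%, so the true risk difference is 8.2 points and the true risk ratio 0.682/0.600 = 1.14. Under a constant hazard, events/N gives a difference of 6.7-7.2 points and a ratio of 1.15. Now take equal hazards, with entry density doubling over the window in one arm only. The crude ratio is then 0.92-0.95 when that arm is the numerator, and 0.99 after balancing on three entry-year bands.

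**5. Death.** With a 60% one-year risk from 1 minus Kaplan-Meier and an assumed yearly mortality of 5-10%, the cumulative incidence is 57-59%.

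**The case against.** The plan is open about its risk: it glosses the term as a proportion of patients, and events/N answers an objective worded that way. It never calls the result a one-year risk. The one-year phrase, "compared to patients treated with Umeclidinium/Vilanterol during the one-year follow-up", belongs to the Cox hazard ratio. All of that stands. A reader may infer a one-year risk from the 365-day cap, but the documents do not claim one, so the point is a missing label and a missing estimate.

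The Risk Ratio row sits in the block of counts and proportions, parallel to the Rate Ratio row, and may simply be the ratio of the two proportions, correctly named. That is also fair. The shells do not show that an odds ratio will be printed there. What they do show is that the logistic result is either mislabelled in that row or has no row at all. The wrong term in the abstract and Section 9.7.1.3 does not depend on which.

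Rates, hazard ratios and the Kaplan-Meier curve already allow for censoring, and the ratio of proportions moves little when entry and disenrollment patterns are alike. This limits the harm but leaves the absolute risks and the risk difference too low. Finally, the size depends on the hazard shape, which is why two shapes are shown.

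**Conclusion.** The point holds for secondary outputs and should be fixed.

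- **Label.** Calling logit output a relative risk is wrong as written. How far it misleads depends on how common discontinuation is: negligible at 5%, material at 50-60% (1.22-1.29 against 1.10).
- **Risk.** Events/N falls below the 365-day risk. The direction follows from the dates and the censoring rule. The size (60% reported as about 45-53% across the two shapes, before disenrollment) rests on assumed risk, uniform entry and hazard shape.
- **Shell error.** The unit and reference value of the risk difference in Tables 4 and 5 are a minor slip.

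Two stronger readings are not supported. One is that the main comparison is compromised: the Cox hazard ratios are not touched by any of this. The other is that the crude risk ratio is seriously biased between arms: that needs different entry or disenrollment patterns, which the documents do not show, and entry year is among the matching covariates.

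**What to change.** - **Logistic results.** Call them odds ratios in the abstract and Section 9.7.1.3, and give them their own row in Tables 4 and 5. If an adjusted relative risk is wanted in the unmatched cohort, estimate it directly by standardisation, that is, by averaging model-predicted risks under each treatment.
- **Crude proportion.** Label events/N as a crude proportion not corrected for censoring.
- **Day-365 risk.** Add risk by arm, risk difference and risk ratio from a cumulative incidence function with death as a competing event. If 1 minus Kaplan-Meier is used instead, say that it treats death as censoring. In the matched cohort, use confidence intervals that respect the matched sets.
- **Event date.** State whether it is the end of supply or the end of the gap. If it is the end of supply, close risk sets 60 days before disenrollment or data end.
- **Treatment switch.** Section 9.3.2.1 excludes switches from the event, but its censoring paragraph does not censor them. Reconcile the two before any risk is computed.
- **Shells.** Give the risk difference per 1,000 patients with reference 0.

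The cost is relabelling and modest code. Reported absolute risks will be higher and intervals slightly wider. With 3,889 against 2 × 3,889 = 7,778 patients (full matching assumed), a hazard ratio of 1.25 and a comparator risk of 60%, a simulation using Kaplan-Meier and ignoring matched sets widened the 95% half-width of the risk difference from 1.9 to 2.2-2.4 points. The risk-ratio interval stayed at about ±4%. If risk sets close early, entrants in the last 60 days (about 1,020 with uniform entry) contribute no risk time, but none of them could have had an event under the current plan.

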Name of active ingredient: Olodaterol and Tiotropium Bromide (ATC R03AL06); Umeclidinium and Vilanterol (ATC R03AL03)			
Protocol date: 22 November 2019	Study number: 1237-0090	Version/Revision: 1.0	Version/Revision date: NA
Research question and objectives:	
This study seeks to compare the differences in treatment persistence in using two combinations of two drugs of the same drug class (LAMA/LABA as a fixed dose combination) delivered through different devices (a DPI or an SMI) within an administrative claims database in the US.
 
The primary objective of the study is to use US data to determine relative treatment persistence between patients prescribed Olodaterol/Tiotropium Bromide delivered with the Respimat SMI and Umeclidinium/Vilanterol delivered with the Ellipta DPI using a 1:2 propensity score matched analysis.
 
The secondary objectives of the study are as follows:
 
 
- Characterize new users of Olodaterol/Tiotropium Bromide and Umeclidinium/Vilanterol in terms of demographics, medication use, comorbidities, and other variables, before and after propensity score matching.
 
- Determine the rate and risk (proportion of patients) of discontinuation among new users of Olodaterol/Tiotropium Bromide and Umeclidinium/ Vilanterol in the 1:2 matched cohort.
 
- Determine the relative rate and risk of discontinuation between Olodaterol/Tiotropium Bromide and Umeclidinium/Vilanterol, using a standard multivariable analysis (Same variables as propensity score model) in the total unmatched cohort.
 
		
Study design:	
New-user cohort design with propensity scores used to match up to 2 Umeclidinium/Vilanterol initiators to each Olodaterol/Tiotropium Bromide initiator.
		
Population:	
Patients initiating Olodaterol/Tiotropium Bromide or Umeclidinium/Vilanterol between 17 November 2015 and 31 March 2018.
 
Exclusion criteria are:
 
 
• Aged <40 years.
 
• Enrolment with medical and pharmacy coverage prior to the cohort entry < 180 days.
 
• Never had COPD diagnosis on the cohort entry date or prior to cohort entry.
 
		

Name of company: Boehringer Ingelheim International GmbH			
Name of finished medicinal product: Stiolto® Respimat®; Anoro® Ellipta®			

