### Matched Cohort

A matched propensity score analysis will be used to assess comparative persistence between the two exposure comparison groups. Logistic regression will be used to calculate the propensity to initiate Olodaterol/Tiotropium Bromide versus Umeclidinium/Vilanterol given all covariates (except components of the Charlson Comorbidity index) listed in [section 9.3.3](#), according to the following model:

$$\text{Logit}(\text{Treatment} | X_1, X_2, \dots, X_n) = \beta_0 + \beta_1 * X_1 + \beta_2 * X_2 + \dots + \beta_n * X_n$$

Any covariates which are collinear with each other will be dropped from the analysis (if it causes failure of model to converge). The propensity score will then be used to identify up to 2 initiators of Umeclidinium/Vilanterol for each initiator of Olodaterol/Tiotropium Bromide with the same propensity score ( $\pm$  a caliper of 5%) as the corresponding initiator of Olodaterol/Tiotropium Bromide (Austin 2011).

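### Matching allows one or two comparators per initiator, but the primary matched HR is a crude, unweighted Cox estimate that can keep part of the measured confounding

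*Combined protocol and SAP*

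**What the plan says.** - **Matching (9.2.2, Matched Cohort).** "The propensity score will then be used to identify up to 2 initiators of Umeclidinium/Vilanterol for each initiator of Olodaterol/Tiotropium Bromide". The abstract describes the design in the same way: "New-user cohort design with propensity scores used to match up to 2 Umeclidinium/Vilanterol initiators to each Olodaterol/Tiotropium Bromide initiator". Closeness is defined by "a caliper of 5%) as the corresponding initiator of Olodaterol/Tiotropium Bromide"; whether 5% is on the score, relative to the score, or in SD of its logit is not stated. Nor are the algorithm, the order of matching, replacement, or whether the two comparators are taken together or in separate rounds.
- **Supply (9.5).** "3,889 initiated Olodaterol/Tiotropium Bromide and 10,862 initiated Umeclidinium/Vilanterol".
- **Matched HR (9.7.1.3).** "Cox proportional hazards models with treatment as the only independent variable will be used to estimate the hazard ratios (HRs) and 95% CIs". The model formula has one common baseline hazard. The abstract says "Crude HRs and 95% CIs will be reported for the matched cohorts". In Annex 5, Table 5, this HR is the only entry in the primary-estimates block, and the primary objective in section 8 is the 1:2 matched comparison.
- **Matched relative risk.** This analysis does use the sets: the abstract has it "as assessed by conditional logistic regression", and the formula in 9.7.1.3 carries a stratum term.
- **Balance (9.7.1.1; Annex 5, Tables 2 and 3).** "Differences in the confounder distributions were inspected for successful confounder balance of measured characteristics". Standardised differences are tabulated for the matched cohort, with no threshold, no action, no match weights and no row for the propensity score.

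**The concern.** When sets hold one or two comparators, initiators and comparators are not represented in the same proportions across the score. Each initiator counts once, but a two-comparator set contributes twice as many comparators as a one-comparator set. If single matches fall mainly where comparators are scarce, that is at high scores, the pooled comparator group is tilted to low scores. A treatment-only Cox model without weights then compares groups that differ on the measured covariates, which is what matching was meant to prevent.

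The estimate at stake is the primary one. In a cohort this large its standard error is small, so a shift of a few hundredths in the HR is not negligible. The matched rates, risks and Kaplan-Meier curves would share the tilt. So would the sensitivity analyses in 9.7.2, which re-report Table 5.

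**Working it through.** **1. The plan's counts.** 3,889 + 10,862 = 14,751, as stated in 9.5. Full 1:2 matching needs 2 × 3,889 = 7,778 comparators, which leaves 10,862 − 7,778 = 3,084 spare. Overall supply is 10,862/3,889 = 2.79 per initiator.

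**2. Local supply.** At score p there are (1 − p)/p comparators per initiator. This is below 2 when p > 1/3. The average treated share is 3,889/14,751 = 26.4%, so a moderate spread in the score puts some initiators above that point.

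**3. What pooling does.** Suppose every initiator is matched and a fraction q has one comparator. Single-match sets hold a share q of the initiators but only q/(q + 2(1 − q)) = q/(2 − q) of the comparators. At q = 0.13 that is 0.13/1.87 = 7% of comparators against 13% of initiators; at q = 0.34 it is 0.34/1.66 = 20% against 34%. With weight 1/k the comparator share is q/(q + 2(1 − q)/2) = q, and the tilt from set size is gone.

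**4. Size, by simulation.** The counts come from the documents; the rest is **assumed**: logit-normal score (SD of logit 0.3, 0.5, 0.7, 1.0), true HR 1.00, one covariate with HR 1.2 per SD, base rate 0.916 per year (1 − e^−0.916 = 60% at one year), other censoring 0.25 per year, greedy nearest matching without replacement, caliper 0.05 absolute. ρ is the correlation of score with outcome risk. Two rounds, random order, 500 runs per cell (Monte Carlo SE of log HR about 0.0012):

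| AUC of score | Initiators with score > 1/3 | Single matches | Crude HR, ρ = 1 / 0.5 / 0.25 | Crude − weighted log HR, ρ = 1 / 0.5 / 0.25 |
|---|---|---|---|---|
| 0.58 | 17% | 2.5% | 1.008 / 1.004 / 1.002 | 0.0048 / 0.0025 / 0.0013 |
| 0.64 | 33% | 13% | 1.020 / 1.010 / 1.006 | 0.0187 / 0.0093 / 0.0044 |
| 0.68 | 44% | 24% | 1.030 / 1.016 / 1.008 | 0.0271 / 0.0133 / 0.0066 |
| 0.74 | 55% | 34% | 1.034 / 1.016 / 1.009 | 0.0314 / 0.0156 / 0.0076 |

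The 1/k-weighted and set-stratified HRs are 1.000 to 1.004 throughout. The unweighted covariate standardised difference is 0.04 to 0.20 at ρ = 1 and 0.02 to 0.09 at ρ = 0.5; weighted, it is 0.01 or less.

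**5. In standard errors.** The SE of the log HR is about 0.026 to 0.030. At AUC 0.74, with SE 0.0285, the part removed by weighting is 0.0314/0.0285 = 1.10 SE (ρ = 1), 0.0156/0.0285 = 0.55 SE (ρ = 0.5) and 0.0076/0.0285 = 0.27 SE (ρ = 0.25). At AUC 0.58, with SE about 0.026, it is 0.18, 0.10 and 0.05 SE.

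**6. Other readings of the plan.**
- Both comparators at once, random order: 0.2% single matches or fewer; crude and weighted log HR agree within 0.0003; HR about 1.00.
- Highest score first, both at once, AUC 0.64, ρ = 1: 0.1% single matches, standardised difference 0.13, crude / weighted / stratified HR 1.021 / 1.021 / 1.020. Weights do not help here. A 0.01 caliper reduces the weighted standardised difference to 0.03 and the weighted HR to 1.001.
- Highest score first, in rounds, AUC 0.74, ρ = 1: crude 1.054, weighted 1.021.
- Caliper read as 5% of the score or 0.05 SD of the logit, two rounds, random order, ρ = 1: 4% to 35% single matches, crude 1.009 to 1.034, weighted 0.998 to 1.001.
- Covariate HR 1.1: crude minus weighted log HR up to 0.017 (ρ = 1) or 0.008 (ρ = 0.5). Covariate HR 1.3: up to 0.045 or 0.022.

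**7. A second, coarser simulation.** With a stronger confounder (log HR 0.4 per SD, perfectly aligned with the score) and group separation of 0.5 to 1.0 SD, matching in rounds (random or highest first) gave crude HRs of 1.03 to 1.13 and weighted HRs of 0.98 to 1.05. Separation of 0.2 SD showed no detectable bias. It used 6 replicates per cell (error about 0.01 to 0.02), so it supports the mechanism and direction, not the size.

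**The case against.** The strongest reply is that no error in this plan has been shown. Set-size bias needs both matching in rounds and a score that separates the groups, and the documents establish neither. What they show is an under-specified algorithm. That is right, and it is why the size above is only an illustration. But the plan as written permits the biased case.

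The effect is also modest. ρ = 1 is a bound: the score uses dozens of covariates, many with no obvious link to refill behaviour. Matching still does most of its work. In a small run (25 replicates) the unmatched HR at ρ = 1 was about 1.09 at AUC 0.64 and 1.16 at AUC 0.74, so the crude matched HR removes about 1 − ln 1.020/ln 1.09 = 77% and 1 − ln 1.034/ln 1.16 = 77% of the confounding. This stands, and it limits the severity.

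Safeguards exist: matched standardised differences, a fully adjusted Cox model in the unmatched cohort, and a set-conditioned matched logistic model. They may reveal a tilt, but no action is tied to them and none of them corrects the primary matched HR.

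Finally, weights alone do not repair highest-first matching. That stands too, so the algorithm, caliper and balance rule belong in the remedy.

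**Conclusion.** The concern holds. The plan allows sets of one or two comparators and analyses them with a crude Cox model that ignores set size, although it conditions on the sets for the relative risk. Depending on match order, rounds, caliper and score overlap, the primary HR can keep part of the measured confounding: none of note with random at-once matching, and up to about 1.1 SE in the worst case of the main illustration (0.1 to 0.55 SE at correlation 0.5). Those figures rest on assumed overlap, confounder strength and event rate, so no bias can be attributed to this study. The change should be made because it is cheap and protects the primary estimate. It is not a demonstrated flaw in a result.

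**What to change.** - **9.2.2:** state the algorithm (for example, greedy nearest-neighbour without replacement, in random order and not from the highest score down), whether the two comparators are taken at once or in rounds, and the caliper scale.
- **9.7.1.3:** estimate the primary matched HR as a marginal HR, weighting each comparator 1/k, where k is the number matched to that initiator, with a robust variance clustered on the matched set. A Cox model stratified by set is acceptable if a conditional HR is intended.
- **Same weights** for the matched standardised differences, Kaplan-Meier curves, rates and risks.
- **Tables 2 and 3:** add a row for the logit of the propensity score, and report how many initiators have 0, 1 and 2 matches.
- **Balance rule:** for example, if any weighted absolute standardised difference exceeds 0.10, tighten the caliper or adjust for that covariate. Adjustment generally changes the estimand from a marginal to a conditional HR, so label it as such.

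**Cost.** One weight, one cluster statement, one rule and a few table rows. The weighted SE was at most about 2% larger than the crude one (0.0290 against 0.0285 at 34% single matches). Stratification costs more: its SE was 16% to 19% above the weighted one (0.0314 against 0.0265 at AUC 0.64). A tighter caliper leaves more initiators unmatched (highest first, AUC 0.64: 4.1% at 0.01 against 0.1% at 0.05). So does at-once random matching (about 24% against 9% in rounds at AUC 0.74, from the 25-replicate run). If nearly all sets hold two comparators, weighting changes almost nothing.
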